7.1. Participant Discontinuation/Withdrawal from The Study

Each subject (or delegate) will be informed of his/her right to withdraw from the study at any time and for any reason. The Investigator may withdraw a subject from the study at any time if he considers that remaining in the study compromises the subject's health.

Additional criteria for discontinuation/withdrawal:

- The insertion of the feeding tube has failed after 3 attempts in each nostril
- Disease progression which requires discontinuation of the study intervention
- If the participant meets an exclusion criterion (either newly developed or not previously recognized) that precludes further study participation.

In the event a subject discontinuation/withdraws from the study the following procedures will be observed:

- The reasons for any subject discontinuation/withdrawal will be recorded on the study completion form of the eCRF.
- The investigator will inform the sponsor of the subject's early withdrawal for any reason.
- If withdrawal is caused by an adverse event that the investigator considers may be related to the device, it will be reported to the IRB and to the Sponsor.

Subjects who signed the informed consent form and are randomized but do not receive the study intervention are considered screen failures and may be replaced. Subjects who sign the informed consent form, and are randomized and receive the study intervention, and subsequently withdraw, or are withdrawn or discontinued from the study may also be replaced.

 ART MEDICAL PATIENT SAFETY TECHNOLOGY	Number: CRO-C-2822	Date issued: 01-Mar-2021
	Rev.06	Page 25 of 35

Subject: smART Plus Comparative Study Protocol - Beilinson

In addition, this study may be temporarily suspended or prematurely terminated if there is sufficient reasonable cause.

Circumstances that may warrant termination or suspension include according to the PI decision, but are not limited to:

- Determination of unexpected, significant, or unacceptable risk to participants
- Demonstration of efficacy that would warrant stopping
- Insufficient compliance to protocol requirements
- Data that are not sufficiently complete and/or evaluable
- Determination that the primary endpoint has been met
- Determination of futility

Study may resume once concerns about safety, protocol compliance, and data quality are addressed, and satisfy the sponsor, IRB and/or Food and Drug Administration (FDA).

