9.1 Sample size consideration

Approximately 200 subjects will be enrolled for the complete multi-center comparative study (100 per group). An interim analysis will be performed after 100 subjects (50 in each group) are enrolled on the primary endpoint.

1- Based on the primary endpoint at interim analysis (feeding efficiency):

Sample size rationale:

The rationale for sample size calculation is based on a difference in feeding efficiency between the tested group (with smART+ System) and the current standard practice (group B).

Sample size justification:

The comparison between groups of food consumption estimations is reflected by Effect size, calculated as the difference between the groups normalized by the common standard deviation.

The calculation uses the following formulation: (Estimation in the tested group - Estimation in control group)/Common standard deviation Error! Bookmark not defined.Error! Bookmark not defined.

A sample size of 50 in each group will have 90% power to detect an **effect size of 0.70** using a two-group t-test with a 0.025 two-sided significance level. [1, 2]

A significance of 0.025 was used instead of the usual 0.05 (alpha adjustment) due to the increase in the chance of making a Type 1 error following two subsequent analysis.

2- Based on the secondary endpoints at end of study:

2.1 Ventilation days:

Sample size rationale:

Subject: smART Plus Comparative Study Protocol - Beilinson

The rationale for sample size calculation is based on a difference in Ventilation days between the tested group (with smART+ System) and the current standard practice (group B).

Sample size justification:

The comparison between groups in ventilation days is reflected by Effect size.

A sample size of 100 in each group will have 90% power to detect an **effect size of 0.46** using a two group t-test with a 0.05 two-sided significance level. [1, 2]

2.2 Ventilation Associated Events:
Sample size rationale:

The rationale for sample size calculation is based on a difference in the proportion of subjects with Ventilation-Associated Events between the tested group (with smART+ System) and the current standard practice (group B) of 20%.

Sample size justification:

A two group continuity corrected c^2 test with a 0.05 two-sided significance level will have 90% power to detect the difference between a Group 1 proportion, p_1 , and a Group 2 proportion, p_2 (**odds ratio of 2.70**) when the sample size in each group is 100.[3]

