2.3 Length of stay:
Sample size rationale:

The rationale for sample size calculation is based on a difference in length of stay between the tested group (with smART+ System) and the current standard practice (group B).

Sample size justification:

The comparison between groups in ventilation days is reflected by Effect size.

A sample size of 100 in each group will have 90% power to detect an **effect size of 0.46** using a two group t-test with a 0.05 two-sided significance level. [1, 2]

References:

9.2 Endpoints analysis:
9.2.1 General:

All measured variables and derived parameters will be listed individually and, if appropriate, tabulated by descriptive statistics.

 ART MEDICAL PATIENT SAFETY TECHNOLOGY	Number: CRO-C-2822	Date issued: 01-Mar-2021
	Rev.06	Page 31 of 35

Subject: smART Plus Comparative Study Protocol - Beilinson

For categorical variables summary tables will be provided giving sample size, absolute and relative frequency and 95% CI (Confidence Interval) for proportions by study arm.

For continuous variables summary tables will be provided giving sample size, arithmetic mean, standard deviation, coefficient of variation (CV%), median, minimum and maximum and 95% CI (Confidence Interval) for means of variables by study arm.

All tests will be two-tailed, and a p value of 5% or less will be considered statistically significant.

The data will be analyzed using the SAS® version 9.4 (SAS Institute, Cary North Carolina).

9.2.2 Primary endpoint:

The two-sample T-test or Non-parametric Wilcoxon-Mann-Whitney Rank sum test for independent samples (as is appropriate) will be applied for testing the statistical significance of the difference in feeding efficiency between the study groups.

9.2.3 Secondary endpoints:

- The two-sample T-test or Non-parametric Wilcoxon-Mann-Whitney Rank sum test for independent samples (as is appropriate) will be applied for testing the statistical significance of the difference in number of ventilation days (Evaluated by the number of hours of etCO2 from the hospital electronic records) between the study groups.

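### The 0.025 level adopted in 9.1 for two analyses of the primary endpoint is not carried into the analysis section, which sets 5% for every test

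*Combined protocol and SAP*

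**What the plan says.** Section 9.1 plans about 200 subjects (100 per group) and an interim analysis of the primary endpoint after 100 subjects (50 in each group). Its first calculation is headed as applying to feeding efficiency at the interim. It claims 90% power for an effect size of 0.70 with 50 per group, "using a two-group t-test with a 0.025 two-sided significance level". The reduction from 0.05 is described as an alpha adjustment, made "due to the increase in the chance of making a Type 1 error following two subsequent analysis". The other calculations in 9.1 are for secondary endpoints at 100 per group and use 0.05. There is no calculation for the primary endpoint at 100 per group.

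Section 9.2.1 sets one rule: "All tests will be two-tailed, and a p value of 5% or less will be considered statistically significant". Section 9.2.2 says that a two-sample t-test or a Wilcoxon-Mann-Whitney test "will be applied for testing the statistical significance of the difference in feeding efficiency between the study groups". It gives no level, and 0.025 appears nowhere in 9.2.

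Section 7.1 lists reasons for suspending or ending the study: "Circumstances that may warrant termination or suspension include according to the PI decision, but are not limited to". The list includes "Demonstration of efficacy that would warrant stopping" and the primary endpoint having been met. It gives no boundary and makes no link to the interim analysis.

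Section 3.1 puts the interim after 50 patients, which does not match 9.1.

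**The concern.** The analysis section governs the test that is actually run. Following it, a statistician would test the final primary endpoint at 5%, without the adjustment that 9.1 makes because of the two analyses. The 0.025 is attached only to the interim calculation, so its use at the final analysis has to be inferred.

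If success can be claimed at the interim at 0.025, a further full 0.05 at the end takes the overall error above 5%. Whatever was intended, two sentences of the plan give different answers for a final p between 0.025 and 0.05. The success criterion of the primary endpoint could then be settled after the result is known, in an open-label trial.

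**Working it through.** **Inputs.** From 9.1: interim at 100 of 200 subjects (information fraction f = 0.50), 50 then 100 per group, two-sided 0.025, effect size d = 0.70. From 9.2.1: two-sided 0.05. From 3.1: interim after 50 patients (f = 0.25 if this is a total).

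**The plan's own figure.** By the normal approximation, d × √(n/2) = 0.70 × √25 = 3.50. The critical value at two-sided 0.025 is 2.241. Power = Φ(3.50 − 2.241) = Φ(1.259) = 89.6%. The exact noncentral t gives 88.8%, and 90% needs 51 per group by the normal approximation. The stated 90% is reproduced closely enough, and it confirms that 0.025 is the level used for the interim at 50 per group.

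**Overall type I error, assuming success can be claimed at either analysis.** With Z1 and Z2 the interim and final statistics, bivariate normal with correlation √f:

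overall error = 1 − P(|Z1| < c1 and |Z2| < c2)

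| Interim level, final level | f = 0.50 | f = 0.25 |
|---|---|---|
| 0.025, 0.025 | 4.28% | 4.65% |
| 0.025, 0.05 | 6.43% | 6.94% |
| 0.05, 0.05 | 8.31% | 9.07% |

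For 0.025 then 0.05 at f = 0.50, c1 = 2.241, c2 = 1.960 and the correlation is 0.707. A simulation of 400,000 null trials with t-tests at 50 and then 100 per group gives 6.5%. The last row takes the 5% rule literally at both analyses. It is the least plausible reading because it ignores the 0.025 in 9.1.

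If no success can be claimed at the interim, the error is that of the final test alone: 5.0% at 0.05.

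**Final level that restores 5% overall after 0.025 at the interim.** Solving the formula for the final level gives 0.0336 at f = 0.50 and 0.0289 at f = 0.25.

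**The affected results.** With 100 per group and a t-test, the smallest significant observed effect size is t(198 df) × √(2/100). This is 0.319 at 0.025, 0.303 at 0.0336 and 0.279 at 0.05. The disputed band is therefore an observed effect size of about 0.28 to 0.32.

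**Power of the final test (noncentral t, 100 per group).** Only 0.70 comes from the plan. The effect sizes 0.50 and 0.40 are assumptions, used to show a range.

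| True effect size | 0.025 | 0.0336 | 0.05 |
|---|---|---|---|
| 0.70 | 99.63% | 99.74% | 99.85% |
| 0.50 | 89.83% | 91.78% | 94.04% |
| 0.40 | 71.53% | 75.41% | 80.36% |

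**The case against.** The best reply is that 0.025 is meant at both analyses. The reason given in 9.1 covers both, halving 0.05 makes sense only if each analysis gets half, and the 5% sentence sits under a general heading and fits the secondary endpoints, which are sized at 0.05. On that reading the specific rule overrides the general one and the overall error is 4.3%. The 6.4% lets 9.1 prevail at the interim and 9.2.1 at the end, and it also needs a success claim at the interim, which the plan never grants. The efficacy grounds in 7.1 are part of a general list with no test or level. At the planned effect size the choice hardly matters: a final p falls between 0.025 and 0.05 about 0.2% of the time (99.85 − 99.63).

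Much of this stands. The plan does not establish that the error is inflated, and 0.025 at both analyses may well be what was intended. But the intention has to be inferred against a rule that covers every test without exception. The interim claim is not far-fetched either: an adjustment for two analyses is needed only if either can yield a claim, 9.1 powers the primary endpoint only at the interim, and 7.1 foresees stopping because that endpoint has been met. If no interim claim is intended, 9.1 and 9.2.1 still need to be reconciled. The small effect on power at 0.70 says nothing about error under the null hypothesis.

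The figures at f = 0.25 rest on the less likely reading of 3.1, where a phrase such as per group may have been dropped. The critical effect sizes apply to the t-test only, while 9.2.2 also allows the rank test.

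**Conclusion.** The concern holds. As written, the final primary test falls under the 5% rule in 9.2.1, without the adjustment made in 9.1, and this has to be corrected. That part rests on the text alone.

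The size is conditional. If success can be claimed at the interim at 0.025, with the interim at 100 of 200 subjects, the written levels give 6.4% overall, and a final p between 0.0336 and 0.05 would be declared significant without support at 5% overall. If 0.025 is meant at both analyses, the error is 4.3% and the disputed band is 0.025 to 0.05. If no interim claim is possible, the error is 5.0% and the adjustment in 9.1 is unnecessary.

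**What to change.** State in 9.2.1 and 9.2.2 that the primary endpoint is tested at two-sided 0.025 at both the interim and the final analysis, and limit the 5% rule to the other endpoints. State whether success can be claimed at the interim. If it can, say that the efficacy grounds in 7.1 apply only at that level.

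There are two acceptable alternatives:

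- Use 0.025 at the interim and a final level computed from the actual information fraction to give 5% overall (0.0336 at one half). The level must be recomputed if the fraction differs: at 0.40, for example, 0.025 then 0.0336 gives 5.2%.
- State that no success claim is possible at the interim, keep 5% at the end, and remove the adjustment from 9.1.

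Separately, reconcile the interim timing in 3.1 with 9.1.

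The cost is a few sentences and no added patients. Using 0.025 instead of 0.05 at the end lowers final power by about 0.2 points at the planned effect size of 0.70. The loss is 4.2 points at an assumed 0.50 (94.04 − 89.83) and 8.8 points at an assumed 0.40 (80.36 − 71.53).

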Measured from admission to ICU until the decision to discharge is ordered.

- Reduction of VAE According to the definition from the latest CDC.
- Decrease in ventilation days.

Evaluated by the number of hours of etCO2 from the hospital electronic records

- Decrease in workload related to nurse GRV time.

Patient GRV information obtained through the hospital's electronic records and the usability questionnaires, will be analyzed to determine (a) the estimated nursing time that was expended for GRV activities, and (b) the amounts of GRV removed from the patient.

- Convenience of use of the system and the user interface (by subjective staff questionnaire)

Evaluated via questionnaires filled by physician users and nurse users participating in the study.

- Assessment of urine flow monitoring related to patient condition and usability

Patient lab results obtained through the hospital's electronic records and the usability questionnaires, will be analyzed against smART+ system urine alerts, to determine if the alerts will be useful in diagnosis and usability satisfaction.

 ART MEDICAL PATIENT SAFETY TECHNOLOGY	Number: CRO-C-2822	Date issued: 01-Mar-2021
	Rev.06	Page 16 of 35
Subject: smART Plus Comparative Study Protocol - Beilinson		

3. Study Design

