4.6. Enrollment

Patients may be included in the study only if:

- The assessment performed as part of the initial screening (part of the eCRF) is acceptable and patient was found appropriate to participate in the trial, according to the PI (or co-investigator) decision.
- Informed consent has been obtained.
- For women of childbearing age, a negative urine (or blood) pregnancy test.

5. Study Intervention

Following the initial screening procedure and after patient was found to be eligible to participate in the study, patients shall be divided into two study groups:

Group A- ICU patients receiving the investigational device ("Treated")

Group B- Control group, receiving treatment according to local SOC.

The study intervention describes all study procedures and evaluations to be done as part of the study to support the determination of the primary and secondary objectives outlined in this protocol. Study source documents are defined as data collected from patient's medical chart (recorded in the hospital sources) as well as data collected by the smART+ System, as detailed in sections 5.2.8. and 5.3.5. below. In addition, video recording (as detailed in sections 5.2.1. and 5.3.1.) will be also used for later data analysis and serves as source data.

Subject: smART Plus Comparative Study Protocol - Beilinson

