5.2.2. Connecting the patient to the smART+ System

The patient should be connected up to all applicable modules of the smART+ as soon as possible after being enrolled in the study. Connection and use of the smART+ UrineFlow system will be as needed according to PI decision.

Detailed instructions of how to connect a patient to the system can be found in the smART+ User Manual and the accompanying Quick Guides.

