The following information will be recorded by the smART+ console (or accompanying recording equipment) and extracted directly by the sponsor:

 ART MEDICAL PATIENT SAFETY TECHNOLOGY	Number: CRO-C-2822	Date issued: 01-Mar-2021
	Rev.06	Page 20 of 35

Subject: smART Plus Comparative Study Protocol - Beilinson

- Urine monitoring: amounts, rates, times, warnings, trends (and all other data collected by the smART+ System).
- Feeding information: Food types, amounts, rate, fluids delivery (and all other data collected by the smART+ System).
- Gastric residual volume: GRV amounts and times
- Reflux and position data
- REE data
- Breathing data (collected by the smART+ System)
- All other data collected by the smART+ System.

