5.3.5. Data recording- group B

The following information will be acquired from the patient's medical chart (recorded in the hospital sources) for each patient:

- Initial screening: as detailed in the study eCRF
- Feeding information: Food types, amounts, rate, water delivery, parenteral nutrition, TPN, Indirect calorimeter and other nutritional data.
- Gastric residual volume: discard gastric residuals amount, GRV procedure times.
- Medications provided: as detailed in the study eCRF.
- Lab results: all patient lab results ordered during the study as well as all available lab results obtained 24 hours prior to study enrollment and added to the eCRF.
- Imaging: patient imaging (X-rays, CT, and alike) performed during the study should be obtained and added to the eCRF.
- Urine monitoring: amounts, rates, times, warnings and all data related to urinary output and diagnosis, and found in the hospital source.
- ICU submission and discharge ordering times
- Breathing data reports starting from the ICU admission (FiO2, PEEP)
- Demographics

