5.5. Schedule of Activities (SoA)

Subject: smART Plus Comparative Study Protocol - Beilinson

Procedures	Screening/ enrollment	Medical Device Placement	Ongoing use	Termination
Day	1	1(T)	Up to 14	1 up to 14
Informed Consent	T+C			
Eligibility Criteria	T+C			
Physical Exam	T+C			
Pregnancy test (if applicable)	T+C			
Videotaping		T+C	T+C	
Vital Signs		T+C	T+C	T+C
REE or calorimeter/spirometer measurement		T+C	T as needed and according to procedures	
Lab Data			T+C	T*+C*
Medical Device Administration		T	T	
GRV Measurements			T+C as needed and according to procedures	
Urine monitoring			T as needed and according to procedures	
Adverse Events	T+C	T+C	T+C	T+C
Concomitant Medication		T+C	T+C	T+C
Information regarding nutritional supplement administration		T+C	T+C	

T – group A – "Treated"

C – group B – "Control"

* - For T only – obtained retroactively 24 hours prior the feeding tube insertion and during the ongoing study

6. Preparation/Handling/Storage/Accountability

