- The two-sample T-test or Non-parametric Wilcoxon-Mann-Whitney Rank sum test for independent samples (as is appropriate) will be applied for testing the statistical significance of the difference in the estimated nursing time that was expended for GRV activities, and the amounts of GRV removed from the patient between the study groups.
- Convenience of use of the system and the user interface scores (by subjective staff questionnaire) will be summarized in an appropriate table by study group
- The two-sample T-test or Non-parametric Wilcoxon-Mann-Whitney Rank sum test for independent samples (as is appropriate) will be applied for testing the statistical significance of the difference in the assessment of urine flow monitoring related to patient condition and usability between the study groups.
- The two-sample T-test or Non-parametric Wilcoxon-Mann-Whitney Rank sum test for independent samples (as is appropriate) will be applied for testing the statistical significance of the difference in ICU length of stay (measured from admission to ICU until the decision to discharge is ordered) between the study groups.
- Chi-square test or Fisher's Exact test (as is appropriate) will be applied for testing the statistical significance of the difference in percent of subjects experiencing Ventilation associated events between the study groups.

9.2.5 Safety:

Adverse events will be coded using the Medical Dictionary for Regulatory Activities (MedDRA, most updated version) terminology and presented in tables by System Organ Class (SOC) and Preferred Term (PT).

Subject: smART Plus Comparative Study Protocol - Beilinson

AE data will be listed individually and summarized by SOC and by PT within a system organ class for each study group.

Frequency of TEAEs (Treatment-Emergent Adverse Events) and device-related adverse events will be summarized in tables by SOC, PT and study group and by seriousness.

Chi-square test or Fisher's Exact test (as is appropriate) will be applied for testing the statistical significance of the difference in percent of subjects experienced any AE, drug-related AE and SAE between the study groups.

Concomitant medications entered into the database will be coded using the World Health Organization (WHO) Drug Reference List, which employs the Anatomical Therapeutic Chemical classification system.

10. Regulatory, Ethical, and Study Oversight Considerations

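### The urine-flow endpoint asks whether smART+ urine alerts are useful in diagnosis, but section 9.2.3 tests it between groups although only group A has such alerts

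*Combined protocol and SAP*

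**What the plan says.** Section 2.2 (Secondary Endpoints) states the purpose of the urine-flow endpoint. Laboratory results and usability questionnaires "will be analyzed against smART+ system urine alerts, to determine if the alerts will be useful in diagnosis and usability satisfaction".

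Section 9.2.3 (Secondary endpoints) gives the analysis: a two-sample t-test or Wilcoxon-Mann-Whitney test, whichever suits, for "testing the statistical significance of the difference in the assessment of urine flow monitoring related to patient condition and usability between the study groups". Section 9.2.1 adds the decision rule: "All tests will be two-tailed, and a p value of 5% or less will be considered statistically significant".

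On who has the data:

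- Section 5 describes the comparator as "Group B- Control group, receiving treatment according to local SOC".
- Section 5.2.8 (group A) lists, among console data, "Urine monitoring: amounts, rates, times, warnings, trends (and all other data collected by the smART+ System".
- Section 5.3.5 (group B) lists, from the medical chart, "Urine monitoring: amounts, rates, times, warnings and all data related to urinary output and diagnosis, and found in the hospital source".
- Section 5.2.2 (group A) says "Connection and use of the smART+ UrineFlow system will be as needed according to PI decision".
- The urine-monitoring row of the Schedule of Activities (5.5) reads "T as needed and according to procedures", with no entry for the control group. The same words also stand in the row for energy-expenditure measurement; the urine row is the one meant here.
- The staff usability questionnaire is section 5.2.9, under group A. Section 5.3 has no counterpart.

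**The concern.** The objective concerns how an alert relates to a reference within a monitored patient: did it fire when the laboratory results showed a problem, and stay silent when they did not? A comparison of group means or ranks does not address that.

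Two things are at stake. A stated objective would go unanswered although group A collects the kind of data it needs. And under the 5% rule in 9.2.1, any small p-value from the planned test would be labelled significant and could be read as evidence that the alerts have diagnostic value.

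**Working it through.** The plan gives no effect size, power or sample size for this endpoint, so there is no figure to reproduce. The check is whether the endpoint, the data and the test fit together.

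**Inputs.** Planned group size is 100 per arm (3.1). smART+ urine alerts come from the console, listed for group A only (5.2.8). The usability questionnaire is listed for group A only (5.2.9). Hospital urine data are listed for both arms (5.2.8, 5.3.5).

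**Candidate readings of the variable to be tested**

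| Reading | Group A | Group B | Consequence |
|---|---|---|---|
| Alerts against laboratory results, as in 2.2 | Patients connected to UrineFlow | 0 of 100 | No comparator |
| Usability questionnaire | Described | Not described | No comparator |
| smART+ alerts in A, hospital warnings in B | Device alerts | Chart warnings | Different quantities in the two arms |
| Hospital urine data in both arms | Available | Available | Computable, but no variable is defined and the question is a different one |

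**First two readings.** The t statistic is (mean A − mean B) / (s × √(1/nA + 1/nB)). With nB = 0, mean B and 1/nB do not exist. For the rank-sum test, U has null mean nA × nB / 2 and variance nA × nB × (nA + nB + 1) / 12. With nB = 0 both are 0, so there is nothing to test.

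**Third reading.** A difference could reflect how a console and a hospital chart generate warnings. It would not show that either kind of warning matched a diagnosis.

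**Fourth reading.** This would ask whether the arms differ in some urine or diagnostic outcome. That is a legitimate randomised question, but not the one in 2.2. The plan supplies no per-patient score, reference diagnosis or time window for it.

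**What a within-group-A analysis could deliver (illustration only).** Assume that acute kidney injury is the target, that true sensitivity is 80%, and that the 30–70% prevalence given for critically ill patients in 1.2.4 applies to whoever is connected. None of these is specified for this endpoint. The Wilson 95% limits are [p + z²/2n ± z√(p(1−p)/n + z²/4n²)] / (1 + z²/n), with p = 0.8 and z = 1.96.

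- All 100 connected: 100 × 0.30 = 30 to 100 × 0.70 = 70 cases. For n = 30: (0.8 + 0.0640 ± 0.1568) / 1.1280, or 63% to 90%. For n = 70: 69% to 88%.
- Half connected (assumed): 15 to 35 cases. For n = 15: 55% to 93%. For n = 35: 64% to 90%.

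These intervals describe the precision of the replacement analysis. They do not measure the defect; the 0 of 100 does.

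**The case against.** The best defence is that 9.2.3 does not say it tests alerts. It repeats the endpoint's title, and group B has urine amounts, rates, times, warnings and diagnosis-related data as well as laboratory results. A diagnostic outcome could therefore be compared between randomised arms. Section 2.2 also already states the alert-versus-laboratory analysis, so one might say that 9.2.3 merely lacks a method.

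Part of this stands. A reader might infer that no between-group urine comparison is possible; section 5.3.5 shows that one could be built. But none is defined, and the one test that is prescribed does not serve the purpose in 2.2. That is a mismatch, not only missing detail.

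Three further inferences go beyond the documents:

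- **That 5.2.2 contradicts itself.** It asks for all applicable modules to be connected and then singles out UrineFlow as discretionary. That is a rule with a stated exception, and the Schedule of Activities agrees with it.
- **That investigators will connect the patients they already suspect.** The study is open-label and the choice is the investigator's, so this is plausible. Section 1.1.5 links automatic urine monitoring to especially susceptible patients, but as a trend in the field. The protocol does not say how patients will be chosen. If such selection did occur, the background prevalence used in the illustration need not hold for the connected patients.
- **That earlier alerts than chart entries would show diagnostic benefit.** Section 1.1.5 says manual checks are at best hourly, so a continuous monitor can lead through sampling frequency alone.

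**Conclusion.** The concern holds as a mismatch between objective and analysis. With 0 of 100 group B patients able to supply a smART+ alert and no usability questionnaire described for that arm, the between-group test has no comparator for the endpoint in 2.2. A p-value obtained from substitute data would not show whether an alert matched a diagnosis.

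This rests only on the protocol's own text. It does not depend on the assumed sensitivity, prevalence or usage. It reaches one secondary endpoint without a power statement; a reader should not carry it over to the primary endpoint or the trial's main conclusion. It is worth correcting because otherwise a stated objective goes unanswered.

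**What to change.** 1. In 9.2.3, replace the between-group test for this endpoint with an analysis within group A patients connected to UrineFlow. Report agreement of alerts with a pre-specified laboratory-based reference diagnosis: sensitivity, specificity and predictive values, with Wilson or exact 95% confidence intervals and allowance for repeated alerts in one patient. Define the alert, the reference and the time window in advance, and confirm that the eCRF laboratory list supports the chosen reference.
2. Summarise usability descriptively for group A.
3. Because 5.2.2 leaves connection to the investigator, report how many group A patients were connected and the recorded reason for non-use in the others. State that the accuracy figures apply to the connected patients.
4. Treat any lead time of alerts over the hospital chart as descriptive only.
5. If a between-group urine outcome is wanted, define it separately from data recorded in both arms.
6. Reconcile the group-A-only urine row in 5.5 with the group B urine data in 5.3.5.

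**Cost.** Wording changes in the protocol and its statistical section, recording of reasons for non-use, and one small extra analysis, largely on data group A already records. The between-group p-value is lost, but for the objective in 2.2 it would not have been informative.
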